9.7 Neurological Risks

The thermal lesioning process with focused ultrasound could cause neurological effects for several reasons. Any effects outside of the treatment area could result in neurologic signs or symptoms. These could occur from the thermal lesioning process that is 'off-target' or

associated infarction, hemorrhage or edema. Subjects will be observed and monitored during the treatment for signs of neurologic side effects. They will also be observed overnight on the neurosurgical ward. Most neurologic side effects would manifest within minutes to hours. Those related to cerebral edema will be transient and expected to resolve within 2-3 weeks.

9.8 Anticipated Treatment Side Effects from MRgFUS

All adverse events will be reported in the Case Report Forms (CRFs) and analyzed for their relation to the ExAblate device as well as other causes (Expected procedure findings, Drug/Contrast media reactions, Medical conditions, and Unrelated to device or procedure). Adverse events related to the device or procedure occur during or shortly after the procedure (within 30 days) since the effect is a one-time, focal treatment. Based on existing treatment experience in the brain using the ExAblate Neuro Type 1.0 (650 KHz), the following anticipated side effects have been identified as possibly occurring during/following the ExAblate procedure.

9.8.1 Procedure-related events include:

- Claustrophobia. Medications may be useful in controlling symptoms, but may also result in nausea/vomiting.
- Pain/discomfort:
 - Sonication-related headache or head/face flushing or warmth. Usually these are transient, but are coincident with a sonication. Headache may occasionally last for several days.
 - Headache may relate to the headframe or fasting status. The brain has no pain sensors, but the scalp, dura and bone tissues do.
 - Position-related pain related to being uncomfortable in the scanner (e.g., sore neck, back pain, muscle or joint pain).
- Hypertension/hypotension, and bradycardia/tachycardia may be related to pre-procedure nervousness or comorbid conditions / missed medication dose pre-procedure as an NPO requirement. Medications can be administered peri-procedure to control them.
- Neurological deficits may result from damage to nearby structures in the brain and thus is specifically related to the target location. To date, the following has been reported:
 - vestibular with or without vegetative manifestations
 - paresthesias
 - dysesthesias/pain.

9.8.2 Events which are Unrelated to the ExAblate device include:

- Events associated with the headframe, such as pin site pain, pin site or scalp/facial edema, pin site burning or bleeding.
- Events associated with the urinary catheter, such as urinary tract infection.

- Events associated with the intravenous line used to administer medications, such as infection and/or bruising.
- Events that are associated with comorbid conditions or unforeseen circumstances.

9.8.3 Drug reactions include:

- Nausea or vomiting
- Dizziness
- Overdose or mis-dosing in error

9.8.4 Events related to malfunction or mis-use of the device include:

- Mis-alignment, mis-targeting or reflection of the ExAblate beam.
- Heating of structures in the FUS backbeam or forebeam
- Additionally, the following side effects are thought to be improbable but their relative risks remain to be defined:

Scalp in the sonication pathway:	Dura, venous sinuses, and cortical veins

 Skin burns ($>2^{\circ}$) with ulceration of the skin Scar formation Loss of sensation Atrophy 	
 Subdural bleeding Vein thrombosis Cortex heating Seizures Symptoms from disturbances of eloquent cortical areas (motor, sensory, auditory, visual, speech)
Bone in the sonication pathway:	

 Bone necrosis 	
Other brain tissue	Cerebral arteries

 Necrosis of normal tissue due to incorrect targeting Thermal damage to adjacent functional brain tissue (e.g.: optical tract) Bleeding in the treated area Cerebral infarction Moderate or severe increase in cerebral edema as shown by MRI scans Symptomatic increase of intracranial pressure Death 	
 Bleeding Coagulation thrombosis Vasospasm Death

Adverse events will be assessed for their relationship to the study device or procedure. Standard Code of Federal Regulation (CFR) definitions for SAEs and UADEs will be used in assessment of adverse events.

Focused Ultrasound thalamotomy has previously been described for essential tremor. These thalamotomies for tremor were performed unilateral to the ventral intermediate nucleus, which is located adjacent to the internal capsule and ventral posterolateral somatosensory nucleus of the thalamus. The medial thalamic target for this study will serve as a central lateral thalamus, and immediately positioned intralaminar nucleus that should not incur risks for sensory, motor, or

cerebellar disturbance. This nocioceptive region of the thalamus will be targeted bilaterally. Acoustic energy will be titrated until peak voxel temperatures at the target reach 55 to 65 degrees Celsius. Intraoperative feedback is less important for this target than for tremor monitoring, so subjects can undergo intravenous sedation for comfort without losing localizing clinical feedback. The postoperative care of medial, CL thalamotomy will be the same as those for Vim thalamotomy with a one day hospital stay.

9.9 Adverse Reactions and Precautions

The subjects will be educated as to what to expect during the procedure and the importance of immediately communicating any problems, unusual symptoms, or discomfort, to the investigator during the treatment and throughout the follow-up period. Subjects will also be educated as to what sensations or perceptions could indicate that neurological damage may be starting to occur. They will be told to use their handheld stop sonication button if they felt anything unusual may be happening so that they can be neurologically assessed. All adverse reactions occurring in this study will be recorded in the Case Report Forms. Each will be assessed for its probable cause (unrelated to the treatment, device related, procedure related, etc) as described below.

9.10 Criteria for Removal from the Study

Subjects can be exited from the study at any time if in the opinion of the principal investigator it is not in the best interest of the subject to carry on as planned. In addition, subjects may also choose to exit the study at any time, but will be strongly encouraged to participate in the follow-up visits for safety reasons (continued monitoring of subject safety).

9.11 Criteria for Stopping the Study

The study will be stopped for evaluation should:

1. any death occur, or
2. if two or more subjects experience
 - a. a cerebrovascular hemorrhage
 - b. or serious related neurological adverse event
 - c. or a 50% increase in pain from Baseline following two consecutive visits starting from 7-days post treatment visit.

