 - Surgical options are quite limited and not amenable to common neuromodulation therapies like spinal cord stimulation or intrathecal narcotics
 - Severely affects functional status and quality of life
2. Focused ultrasound has been demonstrated to be a precise stereotactic lesioning modality, and the technique can be performed without incisions or craniotomy.
3. Medial thalamotomy for the alleviation of nociceptive and neuropathic pains is safe and historical studies have suggested efficacy.
4. Rigorous evidence of neurosurgical interventions for pain relief is lacking, and traditional clinical studies have been confounded by heterogeneous patient populations and uncontrolled studies.

5. The technology is ideal for using sham procedures as a control, and the symptom of pain is extremely susceptible to placebo effects during treatment. Thus a randomized, controlled study is appropriate even at this early stage of investigation.

2.10 Outcome reporting in neuropathic pain:

The Numeric Pain Rating Scale (NPRS) has been shown to be clinically significant when at least a two point change occurs.⁹⁶ Farrar et al suggested this 30% change was clinically meaningful based on its relationship to global assessments of change in multiple studies of chronic pain. The association of the NPRS and the PGIC is highly consistent over multiple trials regardless of the disease, treatment, trial outcome, or patient demographic factors.⁹⁶

The PROMIS inventory (Patient-Reported Outcomes Measurement Information Systems) was developed by the NIH over a decade as a precise set of tools to measure various aspects of health status across patients with varying conditions and especially chronic diseases. From the over 70 domains assessed, pain represents a key component with items addressing: Intensity, Neuropathic and Nocioceptive Quality, Behavior and Interference.

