3.1 Safety

The safety of Exablate lesioning of the bilateral medial thalamus using the ExAblate device will be determined by an evaluation of the incidence and severity of device- and procedure-related complications from the first / treatment day visit through the post-treatment visits. Safety analysis will also include monitoring for any worsening of pain related to painful PN. Events that are neither device- nor procedure-related will be captured and recorded but will not be considered reportable device events unless caused by the device. Relative Safety will be evaluated using a common description of Significant Clinical Complications for patients treated in this study.

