3.2 Efficacy

Outcome assessments will primarily be made at baseline, one, and three months post procedure for patients receiving either the active treatment or sham procedure. Clinical assessments of pain will be made at all clinic visits.

Primary outcome: **safety** as assessed from adverse event reporting and MRI evaluation

Primary efficacy outcome measure will compare the change of **WORST** pain experienced in 24 hours before and at 3 months following bilateral FUS medial thalamotomy versus sham procedures as determined from the 11-point numeric pain rating scale.

Secondary outcome measures will include other patient-reported outcomes including the Global Impression of Change and the Pain Domain from the PROMIS Inventory including items for intensity, quality, behavior and interference.

Imaging assessments will be obtained before and after treatment. The location and precision of the treatment, as well as the volume of the lesion, will be determined from pre- and posttreatment MRI at baseline, 1 day, 1 week, 1 month and 3 months. Functional imaging assessments with Dynamic 2-[¹⁸F] fluoro-2-deoxy-D-glucose Positron Emission Tomography (FDG PET) will be obtained at baseline and three months for each patient. Functional imaging will serve as an objective measure to correlate with clinical pain assessment.

A summary of outcome measures is listed:

Primary (efficacy) outcome: 11-point numeric pain rating scale NPRS (“worst” NPRS score over 24 hours). The change in pain rating from baseline to 3 months posttreatment will be determined and compared between treatment and control cohorts.

Secondary outcomes:

Patient-reported outcome measures:

- PROMIS scale v1.0 – Pain Intensity 3a
- PROMIS scale v2.0 – Neuropathic Pain Quality 5a
- PROMIS scale v2.0 – Nocioceptive Pain Quality 5a
- PROMIS scale v1.0 – Pain Behavior 7a
- PROMIS scale v1.0 – Pain Interference 8a
- Patient Global Impression of Change, 7 point

Functional imaging assessments:

- Dynamic FDG PET

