5.2 Inclusion Criteria

1. Men and women, between 18 and 75 years, inclusive
2. Subjects who are able and willing to give consent and able to attend all study visits
3. Severe chronic, trigeminal neuropathic pain of ≥ 6 months duration.
4. Severity is defined as: Worst NPRS score of ≥ 5 out of 10 at current visit and the subject reports having a similar level of pain for at least the past two months.
5. Pain is medication-refractory to adequate trials of at least 3 prescription medications commonly used for symptomatic relief of neuropathic pain with current adjunctive use of at least one medication. An adequate medication trial is defined as a therapeutic dose of each medication without sufficient effect.
6. Pain is treatment-resistant to at least one interventional therapies including injections, procedures, neuromodulation, and surgery. The interventions trialed depend on the disease and are more specifically defined below:
 - Trigeminal neuropathic pain: failed peripheral injection, percutaneous RF ablation, transcutaneous stimulation, peripheral nerve stimulation, caudalis DREZ lesioning, trigeminal tractotomy, motor cortex stimulation, intraventricular or intrathecal medication infusions, or deep brain stimulation
 - Trigeminal deafferentation pain: pain has resulted from failed trigeminal procedures including percutaneous RF rhizotomy, percutaneous chemical rhizotomy, percutaneous balloon compression rhizotomy, stereotactic radiosurgery, microvascular decompression, or intracranial partial sensory rhizotomy
 - Postherpetic neuralgia of the trigeminal nerve: failed peripheral injection, percutaneous RF ablation, transcutaneous stimulation, peripheral nerve stimulation, caudalis DREZ lesioning, trigeminal tractotomy, motor cortex stimulation, intraventricular or intrathecal medication infusions, or deep brain stimulation
7. Central lateral nucleus of thalamus can be targeted by the ExAblate device. The CL region of the thalamus must be apparent on MRI such that indirect targeting can be performed by measurement from a line connecting the anterior and posterior commissures of the brain.
8. Able to communicate sensations during the focused ultrasound treatment

9. Stable prescribed doses of all symptomatic pain medications for 30 days prior to study entry and for the duration of the 3-month blinded phase of the study.
- 10.

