- d. The final 10-15 minutes of the 60 minute scan will consist of a static FDG PET scan.
- Procedure (sham or treatment).

4. BASELINE ASSESSMENTS:

During the week prior to the procedure, the subject will be provided with time to complete all questionnaires per the schedule of events. These will establish the baseline measures for these particular data points. Baseline assessments include:

- NPRS
- PROMIS measures of pain
- History and physical exam
- Concomitant medications
- Dynamic FDG PET

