8.2 Efficacy

The primary efficacy outcome is the change in worst NPRS score from baseline to 3 months compared between medial thalamotomy and sham procedures with no change or increase in baseline pain medications. A mean change of 2 points has been shown to be clinically significant.⁹⁹ Responder analysis (e.g. number of subjects who have 3-point or better improvement in worst NPRS pain score at 1 and 3 months) will also be performed. Data analyses will also be performed on all PROMIS measures and other subject-reported measures, including PET.

If there is a significant symptomatic pain medication change following MRgFUS treatment, the subject's data will not be used in the Efficacy analysis but the aspects of their procedure will still be included in the Safety analysis.

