9.5 Risks related to bilateral lesioning of central lateral thalamic nucleus

We perceive the following primary risks of bilateral FUS medial thalamotomy based on our review of the historical literature of medial thalamotomy, the extensive experience of CL thalamotomy by our colleague Jeanmonod, and our experience with FUS Vim thalamotomy for ET:

1. Somatosensory deficit & increase pain – from lateral extension of the lesion to VPL
2. Transient cognitive disturbance or confusion
3. Hemorrhagic morbidity – from thermal ablation
4. Cavitation – from focused ultrasound

Somatosensory deficit & increased pain.

Medial thalamic lesions target the intralaminar nuclei and do not result in discriminative somatosensory deficits. Historical lesion of the lateral thalamus (VPM/VPL) often resulted in somatosensory deficits and increased pain due to deafferentation. In order to mitigate this risk, medial thalamic lesions will be confined to the CL nucleus and will not extend laterally to the VPM. The laterality of the coordinates for medial thalamic lesions will be maintained less than 10 mm.

The thermal lesioning process with focused ultrasound could cause **neurological effects** for several reasons. Any effects outside of the treatment area could result in neurologic signs or symptoms. These could occur from the thermal lesioning process that is 'off-target' or

associated infarction, hemorrhage or edema. Subjects will be observed and monitored during the treatment for signs of neurologic side effects. They will also be observed overnight on the neurosurgical ward. Most neurologic side effects would manifest within minutes to hours. Those related to cerebral edema will be transient and expected to resolve within 2-3 weeks.

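### The pain stopping criterion in 9.11 names no scale, and on worst NPRS a 50% rise is impossible from a baseline of 7 or more

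*Protocol*

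**What the plan says.** Section 9.11 lists the events that stop the study for evaluation: any death, or any of three events in two or more subjects. The third of these, 2(c), reads "or a 50% increase in pain from Baseline following two consecutive visits starting from 7-days post treatment visit". It does not say how pain is measured, and no other section ties the rule to an instrument.

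The relevant facts elsewhere in the Protocol are:

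- **Pain instruments.** The visit schedule in section 7.0 has the NPRS and five PROMIS pain forms at Baseline, Day 7, Month 1 and Month 3. Section 3.2 makes the "11-point numeric pain rating scale NPRS" (worst score over 24 hours) the primary efficacy outcome.
- **Entry.** Section 5.2, item 4, asks for a worst NPRS of at least "5 out of 10 at current visit and the subject reports having a similar level of pain" over the preceding two months. There is no upper limit.
- **Baseline.** Section 6.3, item 4, has the questionnaires, NPRS included, completed in the week before the procedure: "These will establish the baseline measures for these particular data points".
- **Meaningful change.** Section 2.10 regards the NPRS as "clinically significant when at least a two point change occurs". Section 8.2 says: "A mean change of 2 points has been shown to be clinically significant".
- **Pain as a safety matter.** Section 3.1 states: "Safety analysis will also include monitoring for any worsening of pain related to painful PN". Section 9.5 puts somatosensory deficit with increased pain first among its primary risks and gives the reason: "Historical lesion of the lateral thalamus (VPM/VPL) often resulted in somatosensory deficits and increased pain due to deafferentation".

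**The concern.** The criterion combines a relative threshold with what is most likely a bounded scale, in a population selected for high scores on that scale. The higher the baseline, the more points a 50% rise requires and the fewer points remain. Beyond some baseline the rule cannot be met however much worse the subject becomes.

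What is at stake is a signal meant to protect later subjects. Criterion 2(c) is the only stopping trigger that names pain, and it needs two subjects in a trial of ten. Every subject who cannot qualify weakens it. Because no scale is named, those applying the rule could also disagree about whether it has been met.

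**Working it through.** The protocol gives no calculation for this rule, so there is no stated figure to reproduce. The check is direct arithmetic.

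**Inputs**

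- Threshold: a 50% increase from Baseline, so the score needed is 1.5 × baseline (section 9.11).
- Scale: worst NPRS, whole numbers 0 to 10 (sections 3.2 and 5.2). That "pain" in 9.11 means this scale is an assumption.
- Entry floor: 5, with no ceiling (section 5.2, item 4).

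**Formulas**

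- Highest baseline at which the rule can be met: 10 / 1.5 = 6.67, so 6 in whole points.
- Largest possible relative rise: (10 − baseline) / baseline.

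| Baseline | Score needed (1.5 × baseline) | Largest possible rise | Can the rule be met? |
|---|---|---|---|
| 5 | 7.5, so 8 (+3) | 100% | yes |
| 6 | 9 (+3) | 66.7% | yes |
| 7 | 10.5 | 42.9% | no |
| 8 | 12 | 25% | no |
| 9 | 13.5 | 11.1% | no |
| 10 | 15 | 0% | no |

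Four of the six scores allowed at entry can never meet the rule. Because Baseline is measured again after the eligibility visit, a Baseline below 5 is possible. The rule works there, and the result for 7 and above does not change.

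**Alternative reading.** If 50% meant 5 points on the scale, a baseline of 6 would need 11, so every baseline of 6 or more would fail. That reading does not rescue the rule.

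**Illustration of the two-subject requirement.** Let *s* be the share of subjects with a baseline of 6 or less. The protocol does not give *s*, so the values below are assumed. The chance that at least two of *n* subjects could qualify at all is 1 − (1 − s)^n − n·s·(1 − s)^(n−1). For n = 5 and s = 0.3 this is 1 − 0.168 − 0.360 = 0.472.

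| Assumed share *s* | n = 5 (one arm) | n = 10 (all subjects) |
|---|---|---|
| 10% | 8% | 26% |
| 20% | 26% | 62% |
| 30% | 47% | 85% |
| 50% | 81% | 99% |

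These are chances that the rule could be met by two subjects, not that it would be.

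**Absolute rules for comparison.** A rise of 2 points is possible from baselines up to 8 (10 − 2), and a rise of 3 points from baselines up to 7 (10 − 3). A 3-point rule leaves the present trigger at 5 and 6 unchanged. From 9 only +1 is possible, and from 10 no NPRS rule can be met.

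**The case against.** The strongest reply is that the ceiling depends on an inference. Section 9.11 says only pain, five PROMIS forms are collected at the same visits, and the protocol gives no score ranges for them. Strictly, what is established is an unnamed scale, and the ceiling is its likely consequence. That is fair, and the conclusion is conditional to that extent. But NPRS is the reading the protocol itself suggests, and a stopping rule whose measure must be guessed needs amending anyway.

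A second reply is that other safeguards cover the gap:

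- Lesion-related pain would normally be recorded as an adverse event, since 9.8.1 lists dysesthesias and pain among procedure-related deficits. The exclusion in 10.0 covers only symptom progression leading to another treatment, so it adds little to the concern.
- A permanent sensory deficit with pain could be serious and count under 2(b).
- The DSMB reviews all adverse events and is asked about unreasonable risk in continuing.

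These points stand in part. What they do not clearly cover is a sustained, non-serious rise in pain. The stop in 10.1 requires an event to be both serious and unexpected, among other conditions, and pain is foreseen. DSMB review otherwise rests on judgement, whereas 2(c) is meant to be automatic.

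Third, the 2-point figure is not a safety threshold. Section 8.2 refers to a mean change and uses 3 points for individual responders. A stopping trigger may reasonably sit above the smallest meaningful change, and the present rule already needs +3 at baselines 5 and 6. This stands: 2 points can be offered only as an example. It does not rescue the current rule, under which a 3-point worsening from 7 cannot count either.

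Finally, the number of subjects affected is not known. That is correct.

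**Conclusion.** The concern holds. Criterion 2(c) names no scale. Read as worst NPRS on whole numbers from 0 to 10, it cannot be met by any subject with a baseline of 7, 8, 9 or 10, and it works at 6 or below. The cut-off is exact under that reading; the reading itself is an inference from the scale's role in eligibility, Baseline and the primary efficacy outcome.

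The defect is confined to the pain trigger. Death, hemorrhage and serious related neurological events still stop the study. The practical size cannot be stated without a baseline distribution, but entry has a floor and no ceiling, so the rule is inactive for those who enter with the most severe pain. A stopping rule belongs in the protocol, so this is not a detail to leave to an analysis plan. It should be fixed.

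**What to change.** Amend 9.11(2)(c) in three respects:

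1. **Name the measure:** worst 24-hour NPRS, compared with the Baseline taken in the week before the procedure.
2. **Replace the relative rise with an absolute one** at two consecutive visits starting from Day 7. Two points or more is one option, in line with sections 2.10 and 8.2. Three points keeps the present sensitivity at baselines 5 and 6 but adds only baseline 7. The sponsor and DSMB should choose.
3. **Add a route that does not use the NPRS** for subjects with no room for that rise: baselines 9 and 10 under a 2-point rule, 8 to 10 under a 3-point rule. A worsened PGIC rating at two consecutive visits would serve, with the cut-off category stated. PGIC is already collected at Day 7, Month 1 and Month 3.

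The cost is a short amendment with DSMB agreement and the usual reporting to the IRB and FDA. No new data are needed. A 2-point rule is more sensitive than the present one at baselines 5 and 6 (+2 instead of +3) and newly active at 7 and 8, so the study might pause for evaluation more often. PGIC is a global rating and could respond to changes other than pain.
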